# 8.3. Withdrawal from the Study

Participants who withdraw from the study after treatment will still be required to complete both follow-up visits as detailed in the SoA.

- A participant may withdraw from the study at any time at his/her own request, or may be withdrawn at any time at the discretion of the investigator for safety, behavioural, compliance or administrative reasons. This applies to withdrawal from the genetic substudy.
- If the participant withdraws consent for disclosure of future information, the sponsor may retain and continue to use any data collected before such a withdrawal of consent. This applies to withdrawal from the genetic substudy.
- If a participant withdraws from the study, he/she may request destruction of any samples taken and not tested, and the investigator must document this in the site study records.
- If a participant is withdrawn from the study every effort must be made to complete the follow-up assessments detailed in the SoA within 7-14 days of last dose and the Day 28 follow-up assessments.

# 8.4. Lost to Follow Up

A participant will be considered lost to follow-up if he or she repeatedly fails to return for scheduled visits and is unable to be contacted by the study site.

The following actions must be taken if a participant fails to return to the clinic for a required study visit:

- The site must attempt to contact the participant and reschedule the missed visit as soon as possible and counsel the participant on the importance of maintaining the assigned visit schedule and ascertain whether or not the participant wishes to and/or should continue in the study.
- Before a participant is deemed lost to follow up, the investigator or designee must make every effort to regain contact with the participant (where possible, 3 telephone calls and, if necessary, a certified letter to the participant's last known mailing address or local equivalent methods). These contact attempts should be documented in the participant's medical record.

• Should the participant continue to be unreachable, he/she will be considered to have withdrawn from the study with a primary reason of lost to follow-up.

#### 9. STUDY ASSESSMENTS AND PROCEDURES

- Study procedures and their timing are summarized in the SoA (Section 2).
- Protocol waivers or exemptions are not allowed
- Immediate safety concerns should be discussed with the sponsor immediately upon occurrence or awareness to determine if the participant should continue or discontinue study treatment.
- Adherence to the study design requirements, including those specified in the SoA, is essential and required for study conduct.
- All screening evaluations must be completed and reviewed to confirm that potential
  participants meet all eligibility criteria. The investigator will maintain a screening
  log to record details of all participants screened and to confirm eligibility or record
  reasons for screening failure, as applicable.
- Procedures conducted as part of the participant's routine clinical management (eg, blood count) and obtained before signing of ICF may be utilized for screening or baseline purposes provided the procedure met the protocol-specified criteria and was performed within the time frame defined in the SoA.
  - The maximum amount of blood collected from each participant over the duration of the study, including any extra assessments that may be required, will not exceed 300mL.
  - Repeat or unscheduled samples may be taken for safety reasons or for technical issues with the samples.

# 9.1. Pharmacodynamics

# 9.1.1. Hemodynamics

Pulmonary arterial catheters will be placed in all participants enrolled. Participants will consent to have the catheter inserted for the purposes of the study. Catheter placement may be confirmed by chest X-ray or fluoroscopy, as clinically indicated. All effort will be made to minimize radiation exposure time.

Variables that will be recorded from the right heart catheterization, as data permit, include:

- right atrial pressure
- pulmonary artery systolic and diastolic pressure
- mean pulmonary artery pressure
- pulmonary wedge pressure
- cardiac output and index measured by thermodilution

- pulmonary vascular resistance (PVR)
- pulmonary artery oxygen saturation (PAsat)

The clinical sites will use their SOPs for the insertion, maintenance and removal of the catheter. The catheter will be removed following completion of the "4 hour post-dose" catheter measurements and sample collections. The participant will then be monitored for a minimum of 20 hours or until discharge.

### 9.2. Adverse Events

The definitions of an AE or SAE can be found in Appendix 4.

The investigator and any designees are responsible for detecting, documenting, and reporting events that meet the definition of an AE or SAE and remain responsible for following up AEs that are serious, considered related to the study treatment or the study, or that caused the participant to discontinue the study (see Section 8).

# 9.2.1. Time Period and Frequency for Collecting AE and SAE Information

- All SAEs will be collected from the signing of the ICF until the follow-up visit at the time points specified in the SoA (Section 2).
- All AEs will be collected from the start of treatment until the follow-up visit at the time points specified in the SoA (Section 2).
- Medical occurrences that begin before the start of study treatment but after obtaining informed consent will be recorded on the Medical History/Current Medical Conditions section of the CRF not the AE section.
- All SAEs will be recorded and reported to the sponsor or designee within 24 hours, as indicated in Appendix 4. The investigator will submit any updated SAE data to the sponsor within 24 hours of it being available.
- Investigators are not obligated to actively seek AEs or SAEs in former study participants. However, if the investigator learns of any SAE, including a death, at any time after a participant has been discharged from the study, and he/she considers the event to be reasonably related to the study treatment or study participation, the investigator must promptly notify the sponsor.
- The method of recording, evaluating, and assessing causality of AEs and SAEs and the procedures for completing and transmitting SAE reports are provided in Appendix 4.

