Frocedure	days before dosing)	Pre- dose 	0h	0.08h (5 min) 	0.5h	1h	2h	4h	8h	24h		uays	
Telemetry			←						→				Monitoring to start 30min prior to treatment administration and continue throughout the study until 24h after dosing
Right heart catheter Insertion		←						<del>)</del>					RHC inserted prior to dose and removed after the 4h hemodynamic measurement
Blood sample for biomarkers of disease activity		Х					Х	Х		Х			
Blood sample for Nitric Oxide		Х					Х	Х		Х			
Blood sample for PK		Х		Х	Х	Х	Х	Χ	Х	Х			
Blood sample for immunogenicity		X									Х	Х	Additional visits may be required. (see Section 9.7 for details).

Procedure	Screening (up to 28				Trea	ntment Pe	riod				Follow- up Day 7- 14	Follow- up Day 28 ± 3 days	Notes
	days before dosing)	Pre- dose 	0h	0.08h (5 min) 	0.5h	1h	2h	4h	8h	24h		auyo	
Blood sample for renin- angiotensin system biomarkers		X		х	Х	Х	X	х	X	х	х		
Blood sample for pulmonary wedge RAS biomarkers		Х				Х	Х	Х					
Hemodynamic measurements		Х				Х	х	х					
Genetic sample		Х											Can be taken any time after consent has been signed. Only required once and is optional.
Discharge										Х			
AE review		←==	======			==>	Х						
SAE review	Х	←==	←										
Concomitant medication review 	Х	Х									Х		

Pre-dose measurements may be taken any time after admission up until dosing.
 Procedures will be completed immediately after dosing has completed.

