# CONFIDENTIAL

Potential Risk of Clinical Significance	Summary of Data/Rationale for Risk	Mitigation Strategy
Potential for Rash	Clinical: In study ACE114622, rash was reported more frequently in subjects receiving GSK2586881, although only one event was considered drug-related.	Participants will be monitored for rash in the clinical trials.
	Study Procedures	
Pulmonary arterial catheterization (PAC)	More common risks of PAC placement include: bruising at the site of the PAC insertion, excessive bleeding, vein injury or tear or pneumothorax. Less common complications include: thrombosis, infection, hypotension, arrhythmia, cardiac tamponade or pulmonary artery rupture.	Insertion of catheter performed by experienced physicians, continuous monitoring of participants during procedure per site standard operating procedures (SOPs).
Exposure to ionzing radiation	Catheter placement may be confirmed by chest X-ray or fluoroscopy, as clinically indicated. Both chest X-ray and fluoroscopy are assumed to increase the risk of cancer or heritable effects due to radiation exposure. Radiation exposure from chest X-ray is minimal (0.02mSv). Radiation exposure from fluoroscopy used to confirm placement of the catheter is dependent on the equipment and duration of the procedure. The dose will typically be around 2mSv but may range from 2-5mSv. The additional risk of developing a fatal malignancy (cancer) as a result of these exposures has been estimated as between 1 in 10,000 and 1 in 2000 for an adult in normal health.	Negative pregnancy testing prior to procedure. Minimize fluoroscopy time; lead shielding per site SOPs. Maximum exposure will not exceed 10mSv to confirm placement of the catheter.

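### Non-serious complications of the study catheter that begin and are recognised before dosing are recorded as medical history, not as adverse events

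*Protocol*

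**What the plan says.** On the catheter, Section 9.1.1 states: "Pulmonary arterial catheters will be placed in all participants enrolled". It adds: "Participants will consent to have the catheter inserted for the purposes of the study". The Schedule of Activities gives the timing: "RHC inserted prior to dose and removed after the 4h hemodynamic measurement". The study-procedures part of the risk table in Section 3.3.1 reads: "More common risks of PAC placement include: bruising at the site of the PAC insertion, excessive bleeding, vein injury or tear or pneumothorax". It lists thrombosis, infection, hypotension, arrhythmia, tamponade and pulmonary artery rupture as less common.

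On collection, Section 9.2.1 sets three rules.

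- Serious events: "All SAEs will be collected from the signing of the ICF until the follow-up visit at the time points specified in the SoA (Section 2").
- Adverse events generally: "All AEs will be collected from the start of treatment until the follow-up visit at the time points specified in the SoA (Section 2").
- The interval from consent to dosing: "Medical occurrences that begin before the start of study treatment but after obtaining informed consent will be recorded on the Medical History/Current Medical Conditions". That rule ends by excluding the AE pages of the CRF.

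Appendix 4 defines an AE by its temporal association with study treatment. It requires an intensity grade and a judgement of relationship to study treatment for each AE and SAE.

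**The concern.** The protocol treats catheter placement as a risk of taking part and lists its complications. Its recording rule then files the milder ones, if noticed before the dose, alongside conditions the participant brought into the study. Harm caused by a study procedure is thus recorded as pre-existing.

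Three consequences follow from the text.

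- The event receives no AE intensity grade and no causality judgement.
- Section 9.5.5 databases telemetry findings only as AE or SAE data, and telemetry starts 30 minutes before dosing. A non-serious catheter-induced arrhythmia in that half hour is not a collected AE, so its telemetry record has no route into the database as one.
- The cardiovascular event page in Appendix 4 is tied to AEs and SAEs. A pre-dose arrhythmia filed as history would not prompt it by that route.

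At stake is the completeness of the procedure-risk record, which Section 3.3.1 makes part of the risk assessment. An analysis plan cannot repair this later, because attributes that were never collected cannot be tabulated.

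**Working it through.** The protocol states no figure to reproduce. The check sets the collection windows against the timing of the catheter.

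**Step 1: order of events.** Consent, then catheter insertion, then dosing, then catheter removal after the 4-hour measurement (Section 9.1.1; Schedule of Activities). SAE collection opens at consent and AE collection at the start of treatment (9.2.1). Insertion therefore falls where only SAEs are collected.

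**Step 2: what start of treatment means.** Section 7 gives a generic definition of study treatment that mentions medical devices, but Section 7.1 lists only GSK2586881. Start of treatment is therefore the dose, not the catheter.

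**Step 3: where each kind of catheter complication goes.**

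| Complication | Recorded as | Source |
|---|---|---|
| Serious, from consent onward | SAE | 9.2.1 |
| Non-serious, begins after dosing (including at removal) | AE | 9.2.1 |
| Non-serious, present before dosing but first detected after | AE | Appendix 4 |
| Non-serious, known before dosing, worsens after | AE | Appendix 4 |
| Non-serious, begins and is recognised between insertion and dosing, does not worsen | Medical history | 9.2.1 |

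Only the last row is outside the AE data.

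**Step 4: search for an exemption.** Section 9.2 mentions events related to the study, but only for follow-up of AEs; it does not move the start of collection. Neither the AE definition nor the causality rule in Appendix 4 mentions procedures. The Safety population in Section 10.2 requires a dose, so someone catheterised but never dosed falls outside it. No exemption was found.

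**Step 5: two loose ends in the text.** The medical-history rule is not limited to non-serious events, so read literally it overlaps the SAE rule. The AE rule also points to the Schedule of Activities, where the arrow for AE review appears to begin in the pre-dose column. The extracted table is broken, so nothing is rested on it; if that is the true layout, it conflicts with 9.2.1.

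**Step 6: scale, for illustration only.** Let p be the chance that a participant has an event in the last row of the table. The protocol gives no value, so p is assumed from 1% to 30%. Take n = 4 × 4 = 16 (four cohorts at minimum size) and n = 27 (maximum completers, Section 5.2). Expected number = n × p; chance of at least one = 1 − (1 − p)^n.

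| p (assumed) | n = 16: expected; chance of ≥1 | n = 27: expected; chance of ≥1 |
|---|---|---|
| 1% | 0.16; 15% | 0.27; 24% |
| 5% | 0.80; 56% | 1.35; 75% |
| 10% | 1.6; 81% | 2.7; 94% |
| 20% | 3.2; 97% | 5.4; 99.8% |
| 30% | 4.8; 99.7% | 8.1; >99.9% |

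The range is too wide to support any single estimate.

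**The case against.** The best defence is that the rule is a coherent choice. The secondary safety objective concerns single doses of GSK2586881, not catheterisation. The AE definition and the causality assessment are tied to study treatment, and 9.2.1 agrees with both. With no placebo arm, keeping pre-dose events apart from post-dose events helps attribution to the drug. The events are also not lost: they stay in the CRF under another heading.

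Much of this stands, and it rules out two stronger readings.

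- A reader might infer that catheter harm in general goes unreported. The documents do not support that. Serious complications are collected from consent, and those that begin, are first detected or worsen after dosing are AEs.
- A reader might infer that the rule distorts the baseline for judging the drug. That is not supported either: a condition present before the dose is pre-dose status whatever caused it. The analysis of the drug's safety would be the same after the fix.

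What the defence does not answer is that the protocol itself lists placement complications as study risks, yet leaves the mild, early ones ungraded and indistinguishable by form from the participant's own history. Separation from post-dose events can be had without that loss.

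**Conclusion.** The point holds in a limited form. As written, 9.2.1 places one class of study-caused event outside the AE data: non-serious catheter complications that begin and are recognised between insertion and dosing. This follows from the text and needs no assumption about rates. All enrolled participants are subject to the rule, but only those who have such an event are affected, and how many cannot be said. It would be tempting to quote a count out of 27, but the protocol offers no basis for one. The consequence is a less complete record of procedure risk, not a flaw in the assessment of GSK2586881. The possible mismatch with the Schedule of Activities is conditional on the layout of the source table.

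**What to change.** Amend Section 9.2.1 to say that AEs judged related to a study procedure are collected from catheter insertion, with intensity and relationship to the procedure recorded, and listed separately as pre-dose procedure-related events. Include anyone catheterised but not dosed. State that other pre-dose non-serious events stay in Medical History, which also removes the overlap with the SAE rule. Treatment-emergent tables continue to start at dosing.

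Check where the AE review row of the Schedule of Activities begins and make it agree with the amended text.

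The cost is one sentence in 9.2.1, slightly more AE data entry with a relationship-to-procedure field, and one extra listing.

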# 9.2.2. Method of Detecting AEs and SAEs

Care will be taken not to introduce bias when detecting AE and/or SAE. Open-ended and non-leading verbal questioning of the participant is the preferred method to inquire about AE occurrence.

## 9.2.3. Follow-up of AEs and SAEs

After the initial AE/SAE report, the investigator is required to proactively follow each participant at subsequent visits/contacts. All SAEs, will be followed until the event is resolved, stabilized, otherwise explained, or the participant is lost to follow-up (as defined in Section 8.4). Further information on follow-up procedures is given in Appendix 4.

## 9.2.4. Regulatory Reporting Requirements for SAEs

- Prompt notification by the investigator to the sponsor of a SAE is essential so that legal obligations and ethical responsibilities towards the safety of participants and the safety of a study treatment under clinical investigation are met
- The sponsor has a legal responsibility to notify both the local regulatory authority and other regulatory agencies about the safety of a study treatment under clinical investigation. The sponsor will comply with country-specific regulatory requirements relating to safety reporting to the regulatory authority, IRB/ IEC, and investigators.
- Investigator safety reports must be prepared for suspected unexpected serious adverse reactions (SUSAR) according to local regulatory requirements and sponsor policy and forwarded to investigators as necessary.
- An investigator who receives an investigator safety report describing a SAE or
  other specific safety information (eg, summary or listing of SAE) from the
  sponsor will review and then file it along with the IB and will notify the
  IRB/IEC, if appropriate according to local requirements.

#### 9.2.5. Cardiovascular and Death Events

For any CV events and all deaths, whether or not they are considered SAEs, specific CV and Death sections of the CRF will be required to be completed. These sections include questions regarding CV (including sudden cardiac death) and non-CV death.

The CV CRFs are presented as queries in response to reporting of certain CV medical dictionary for regulatory activities (MedDRA) terms. The CV information should be recorded in the specific CV section of the CRF within one week of receipt of a CV Event data query prompting its completion.

The Death CRF is provided immediately after the occurrence or outcome of death is reported. Initial and follow-up reports regarding death must be completed within one week of when the death is reported.

## 9.2.6. Pregnancy

- Details of all pregnancies in female participants and, if indicated, female partners of male participants will be collected after the start of study treatment and until 1 week after dose.
- If a pregnancy is reported, the investigator should inform GSK within 24 hours of learning of the pregnancy and should follow the procedures outlined in Appendix 5.
- Abnormal pregnancy outcomes (eg, spontaneous abortion, fetal death, stillbirth, congenital anomalies, and ectopic pregnancy) are considered SAE.

#### 9.3. Treatment of Overdose

For this study, any dose of GSK2586881 greater than 1.2mg/kg will be considered an overdose.

Sponsor does not recommend specific treatment for an overdose.

In the event of an overdose, the investigator/treating physician should:

- 1. Contact the Medical Monitor immediately.
- 2. Closely monitor the participant for AE/SAE and laboratory abnormalities until GSK2586881 can no longer be detected systemically (at least 3 days post last dose).
- 3. Obtain a plasma sample for PK analysis as described in the SoA (Section 2). PK assessments may be continued beyond 24 hours if requested by the Medical Monitor (determined on a case-by-case basis).
- 4. Document the quantity of the excess dose as well as the duration of the overdosing in the CRF.

Decisions regarding dose interruptions or modifications will be made by the investigator in consultation with the Medical Monitor based on the clinical evaluation of the participant.

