#### 5.5. Dose Justification

GSK2586881 has been studied in 21 healthy subjects as single, intravenous doses over 30 minutes from 0.1 mg/kg to 1.2 mg/kg, and in repeated daily doses for up to six days of 0.4 mg/kg once a day. In addition, ARDS patients have received four doses of GSK2586881: 0.1 mg/kg, 0.2 mg.kg, 0.4 mg/kg and 0.8 mg/kg over a 24 hour period (n=5) or 0.4 mg/kg BID for 3 days (n=19).

A preliminary population PK model for GSK2586881 has been derived from data obtained in healthy subjects and ARDS patients and showed that the systemic PK profile was adequately described by a two-compartment first order elimination model and that the PK profile was independent of population (healthy subjects or ARDS patients). Decreases in Ang II levels occurred rapidly after GSK2586881 administration with Ang II concentrations maximally or near maximally reduced at the first sampling time of 5 minutes post-dose; consistent with maximal plasma concentrations of GSK2586881. The PK/PD response (the relationship between ACE2 and Ang II) in healthy subjects and ARDS patients appeared to be best described with a single direct Emax model after accounting for differences in baseline Ang II concentrations between healthy subjects and ARDS patients. The observation of no significant delay between GSK2586881 concentration and effect is in line with its mechanism of action as an enzyme on a substrate.

Based on the preliminary population PK/PD model described above, it is predicted that following a single dose of ≥0.2 mg/kg, Ang II concentrations will on average be reduced below participant baseline levels for at least 24 hours post-dose (assuming Ang II levels in PAH participants is consistent with levels reported in ARDS participants in GSK study ACE114622 (GSK Document Number 2014N217963\_00). The 0.8mg/kg dose has been selected to investigate the safety and tolerability dose range for GSK2586881 in this patient population.

In an investigator-sponsored study (NCT01884051) GSK2586881 has been studied in 3 PAH patients as a single, intravenous dose at 0.2 mg/kg, and in 2 patients at 0.4mg/kg. There were no SAEs and no dose limiting toxicities were observed.

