## 7.1. Treatments Administered

Study Treatment Name:	GSK2586881
Dosage formulation:	Clear, colorless liquid
Unit dose strength(s)/Dosage level(s):	Unit dose strength: 5 mg/mL Up to 0.8mg/kg
Route of Administration	IV
Dosing instructions:	IV push over 3-5 minutes
Packaging and Labeling	Study Treatment will be provided in frozen vials. Each vial will be labeled as required per country requirement.
Manufacturer	Polymun/GSK

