#### 7.2. Dose Modification

The study will comprise of 4 separate cohorts. Participants will be administered a single dose of one of the following planned doses: 0.1, 0.2, 0.4, or 0.8mg/kg.

Dose escalation will occur after a minimum of 4 participants have been dosed per cohort and review of safety, tolerability, PK and hemodynamic data up to 24h post dose has taken place. Dose escalation will continue up to a maximum dose of 0.8mg/kg.

Cohort sizes may vary with a minimum of 4 participants per cohort. Additional participants may be enrolled to expand a dosing cohort to further evaluate findings at a given dose level.

If a subject experiences a dose limiting toxicity (DLT) that is considered at least possibly related to study drug, dosing of additional participants will be halted and a full safety review will be performed to confirm causality. If 2 participants in any cohort experience

a DLT considered at least possibly related to study drug, the maximum tolerated dose (MTD) has been exceeded.

Dose limiting toxicities are defined as toxicities that, due to their severity or duration, are considered unacceptable, and limit further dose escalation. Examples of DLT's include, but are not limited to:

- Severe headache unrelieved by nonsteroidal anti-inflammatory drugs (NSAIDS)
- Nausea/Vomiting
- Hypotension as defined by mean arterial pressure <60mmHg or a drop in systolic BP of 25%

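### Section 9.3 counts only doses above 1.2 mg/kg as overdose although the study maximum is 0.8 mg/kg, so an asymptomatic dose in between triggers neither a Medical Monitor call nor 3-day monitoring

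*Protocol*

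**What the plan says.** Section 7.1 gives the dosage level as up to 0.8 mg/kg, given as "IV push over 3-5 minutes". Section 7.2 lists the planned doses as 0.1, 0.2, 0.4 and 0.8 mg/kg and states: "Dose escalation will continue up to a maximum dose of 0.8mg/kg". The Synopsis repeats this.

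Section 9.3, speaking of this study in particular, states that "any dose of GSK2586881 greater than 1.2mg/kg will be considered an overdose". Four actions follow, all conditional on an overdose. The first is "Contact the Medical Monitor immediately". The second is close monitoring until the drug can no longer be detected, which is put at "at least 3 days post last dose". The third is a PK sample and the fourth is a CRF record of the excess.

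Section 5.5 describes prior experience. Healthy subjects received "single, intravenous doses over 30 minutes from 0.1 mg/kg to 1.2 mg/kg". An investigator-sponsored study treated "3 PAH patients as a single, intravenous dose at 0.2 mg/kg, and in 2 patients at 0.4mg/kg". ARDS patients received four rising doses up to 0.8 mg/kg within 24 hours (n=5), or 0.4 mg/kg twice daily for 3 days (n=19).

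**The concern.** An overdose section exists so that an excess dose prompts action by itself, before anyone has noticed a symptom. Here the trigger sits above the highest dose that the study allows, and no section explains the distance.

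The case that matters is a dosing error without symptoms. Under the Schedule of Activities, telemetry and the in-house stay end at 24 hours and the next visit is on Day 7-14. Adverse event reporting does not fill the gap: under Appendix 4, an overdose without signs or sequelae is not reported as an AE or SAE unless it was intentional, with possible self-harm. At stake is prompt medical oversight of a participant who has received more than the study permits. No estimate or analysis is at stake.

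**Working it through.** There is no calculation behind the 1.2 mg/kg figure to reproduce. The check sets the sections side by side and measures the gap.

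**Inputs.** Overdose threshold 1.2 mg/kg (9.3). Maximum dose 0.8 mg/kg and planned doses 0.1, 0.2, 0.4 and 0.8 mg/kg (7.1, 7.2). Unit strength 5 mg/mL (7.1). Body weight at most 100 kg (6.1, criterion 10).

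**Width of the band.** 1.2 − 0.8 = 0.4 mg/kg, and 1.2 / 0.8 = 1.5. At 100 kg the band runs from above 0.8 × 100 = 80 mg to 1.2 × 100 = 120 mg, that is, from above 80 / 5 = 16 mL to 120 / 5 = 24 mL.

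**Error needed to land in the band.** Lower limit = 0.8 / assigned dose. Upper limit = 1.2 / assigned dose.

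| Cohort (mg/kg) | More than | Up to |
|---|---|---|
| 0.1 | 8-fold | 12-fold |
| 0.2 | 4-fold | 6-fold |
| 0.4 | 2-fold | 3-fold |
| 0.8 | 1-fold | 1.5-fold |

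As an illustration, a tenfold error in the 0.1 cohort gives 1.0 mg/kg. At 100 kg, 0.1 × 100 / 5 = 2 mL was intended and 1.0 × 100 / 5 = 20 mL was given. That exceeds every planned dose and is still not an overdose under Section 9.3.

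**What applies to an asymptomatic participant.**

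| Step | Above 0.8, up to 1.2 mg/kg | Above 1.2 mg/kg |
|---|---|---|
| Immediate Medical Monitor contact | Not required | Required (9.3) |
| Close monitoring for at least 3 days | Not required | Required (9.3) |
| Dose recorded in source and CRF | Yes (7.6) | Yes (7.6, 9.3) |
| Telemetry, vital signs and PK to 24 h | Yes (Schedule of Activities) | Yes |
| PK sampling beyond the schedule | Possible (9.6) | Possible (9.3, 9.6) |
| Repeat of clinically significant laboratory abnormalities | Yes (9.5.6) | Yes (9.5.6) |

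Only the first two rows differ materially.

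**Would a bare threshold of 0.8 mg/kg work?** Not in the 0.8 cohort. At 57 kg the intended volume is 0.8 × 57 / 5 = 9.12 mL. Rounded to 9.2 mL, the dose is 9.2 × 5 / 57 = 0.807 mg/kg, so ordinary rounding would count as overdose. With a 10% tolerance the line is 0.8 × 1.1 = 0.88 mg/kg. The rounding example then passes and the 1.0 mg/kg example is still caught.

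**The case against.** The strongest reply is that the two figures do different jobs: Section 7.2 limits escalation and Section 9.3 says when special handling begins, so they need not agree. On this reading 1.2 mg/kg is a sensible line, because it is the highest single human dose that the protocol cites. Section 3.3.1 reports no adverse hemodynamic or blood pressure effects in the healthy-volunteer study, and Section 3.3.3 reports no treatment-related clinically significant changes in vital signs or ECG at any dose. The Investigator's Brochure, the protocol deviation plan or the study reference manual may also cover the matter; none is at hand.

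Part of this stands. The threshold may be deliberate, so it cannot be called an error. But the protocol does not give this reason, and the 1.2 mg/kg experience was a 30-minute infusion in healthy subjects.

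The existing cover is also real. The catheter stays in until the 4-hour measurements, a possibly related dose-limiting toxicity halts further dosing (7.2), signs of a suspected overdose are adverse events (Appendix 4), and immediate safety concerns go to the sponsor (Section 9). Section 7.6 requires a second person to confirm both a preparation from bulk supply and the dose at administration. These safeguards are either routine or depend on someone noticing a problem. None makes the excess dose itself the trigger.

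A reader might go further and infer that the band is shown to be hazardous, because it lies far from patient experience. The ratios do not support that:

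- **Rate.** The cited infusion ran at 1.2 / 30 = 0.04 mg/kg/min. A 1.2 mg/kg push gives 1.2 / 5 = 0.24 to 1.2 / 3 = 0.40 mg/kg/min, 6 to 10 times as fast. The planned 0.8 mg/kg push already gives 0.8 / 5 = 0.16 to 0.8 / 3 = 0.27 mg/kg/min, 4 to 6.7 times as fast.
- **PAH experience.** 1.2 mg/kg is 1.2 / 0.4 = 3 times the highest PAH dose cited, but the planned 0.8 mg/kg is already 0.8 / 0.4 = 2 times.

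Both arguments apply to the approved top cohort too, so neither singles out the band. A reader might also infer from the amendment history in Appendix 8 that 1.2 mg/kg is a leftover from a former top dose. That history does not say why Section 9.3 uses the figure, and the point rests on current text alone.

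**Conclusion.** The point holds as a minor safety improvement. Doses above 0.8 and up to 1.2 mg/kg, at most 1.5 times the study maximum, lie outside the overdose definition. Without symptoms, such a dose triggers neither the immediate call nor the monitoring for at least 3 days. The reason to move the line is that 0.8 mg/kg is the most the study permits, not that the documents show harm between 0.8 and 1.2 mg/kg; they do not.

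This rests on two assumptions: that Section 9.3 is the only place where an excess dose by itself prompts these two actions, which is so in the protocol but cannot be checked in the unseen manuals, and that the two staff checks have failed. How often that would happen cannot be estimated from the protocol. No endpoint, population or analysis changes.

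**What to change.** In Section 9.3, define overdose as any dose above 0.8 mg/kg beyond a small preparation tolerance. The clinical team should set the tolerance; 10% is an example and would put the line at 0.88 mg/kg.

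Optionally, add one sentence: a dose that exceeds the assigned cohort dose by more than the same tolerance but is not above 0.8 mg/kg requires Medical Monitor contact and a record of the excess, with extended monitoring at the Medical Monitor's discretion. A mix-up that ends at a planned dose would then not automatically bring 3 days of monitoring. The two lines should be worded to meet, so that the tolerance leaves no gap between them for the lower cohorts.

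The cost is one changed threshold, at most one added sentence in the next amendment, and a decision on the tolerance. The downside is an occasional extra call and follow-up.
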